3.4 Treatments

3.4.1 Details of Study Treatments

Information about the study drugs is provided in Table 6 below.

Table 6: Details of the Study Drugs

	Study drug	Placebo
Name	AGB101	Not applicable
Manufacturer	AgeneBio, Inc.	AgeneBio, Inc.
Dose(s)	1 x 220 mg	Not applicable
Route	Oral	Oral
Formulation	Light yellow to peach coated capsule shaped tablet debossed with "AGB"	Light yellow to peach coated capsule shaped tablet debossed with "AGB"
Strength(s)	220 mg	Not applicable

AGB101 = low-dose levetiracetam, 220 mg, extended release.

The sponsor will provide all the drug supplies. Subjects will be receiving AGB101 or placebo in the morning in identically appearing oral dosage forms. One dose of AGB101

Confidential Page 44 of 95

will contain 220 mg of levetiracetam. A 102-day supply will be provided at each of the clinical visits.

3.4.2 Dosage Schedule

Subjects will be administered a single morning daily dose of placebo or AGB101 for 78 weeks. Given the low dose being used, AGB101 dosing will be initiated without titration and will be discontinued without tapering.

3.4.3 Treatment Assignment (1:1 Randomization Placebo:AGB101)

A central randomization list will be used for the treatment assignment.

After signing informed consent, subjects will be assigned a unique 10-digit subject identification number (XXX-CC-SSS-EE), with the first 3 digits for the study, the next 2 digits for the country, the next 3 digits for the site, and the last 2 digits for the sequential order of enrollment at a given site. Subjects who are rescreened will receive a new identification number; the previous number will also be recorded by the site. After screening assessments are performed and eligibility is confirmed, eligible subjects will be randomized at baseline. Randomization will be accomplished by the study site using an interactive web response system (IWRS) to assign the next sequential randomization number within the relevant stratum to the eligible subject. Block randomization will be used at each site, with each block having a randomly chosen length of 4 or 6 (each with probability 1/2).

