Investigator(s)/Study Center(s):	This study will be conducted at approximately 98 study sites in the Americas and Europe. Worldwide Clinical Trials, a contract research organization, will oversee operational aspects of this study on behalf of AgeneBio, Inc., the sponsor of the study.	
Phase of Development:	Phase 2B	
Objectives:	The objectives of this study are as follows:	
	Primary objective	
	To assess the efficacy of AGB101 (low-dose levetiracetam, 220 mg, extended release tablet) compared to placebo in subjects with mild cognitive impairment (MCI) due to Alzheimer's disease (AD) using Clinical Dementia Rating-Sum of Boxes (CDR-SB) scores.	
	Secondary objectives	
	To assess the efficacy of AGB101 compared to placebo on daily functioning and cognition using Functional Activities Questionnaire (FAQ) and Mini Mental State Examination (MMSE) scores.	
	To assess the effect of AGB101 compared to placebo on neuronal injury, as measured by a change in the entorhinal cortex (EC) thickness, using magnetic resonance imaging (MRI).	
	Additional secondary objectives	
	To assess the efficacy of AGB101 compared to placebo using CDR (global, memory box), Behavioral Pattern	

Confidential Page 3 of 95

	Separation-Object (BPS-O) task, and International Shopping List Test (ISLT) scores.
	To assess the effect of AGB101 compared to placebo on hippocampal volume using MRI.
	• To assess the effect of AGB101 compared to placebo on the levels of tau protein in the brain using the tau positron emission tomography (PET) marker 6-[¹⁸ F]fluoro-3-(1H-pyrrolo[2,3-c]pyridin-1-yl)isoquinolin-5-amine ([¹⁸ F]MK-6240) in a subpopulation of approximately 56 subjects.
	Exploratory Objective
	To assess the effect of AGB101 on blood-based biomarkers of neurodegeneration using samples collected at week 78 or the early termination visit.
	Exploratory Objective (optional procedure to be performed only at Johns Hopkins University)
	To assess the efficacy of AGB101 compared to placebo on hippocampal overactivity in subjects with MCI due to AD.
	Safety objective
	To assess the safety and tolerability of AGB101 compared to placebo in subjects with MCI due to AD.
Study Design:	This is a multicenter, randomized, double-blind, placebo- controlled, 78-week, fixed-dose study evaluating AGB101 versus placebo as a treatment for slowing the progression of MCI due to AD.
Planned Sample Size:	A total of 160 subjects will be randomized (80/treatment group).
Subject Selection	Eligibility criteria

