Statistical Analyses:	The primary goal of the study is to estimate the average treatment effect defined as the difference between the population mean outcome of the primary endpoint (CDR-SB change score from baseline to 78 weeks) comparing treatment to control. The primary null hypothesis is that the average treatment effect is zero. The alternative hypothesis is that the average treatment effect is not equal to zero.
	In the primary analysis, we will use a pre-specified, intention-to-treat estimator that simultaneously (i) adjusts for 78-week outcomes missing at random (due to subject loss to follow up), and (ii) adjusts for chance imbalances in key baseline variables between the study arms. One advantage of this estimator is that it is consistent under weaker assumptions on missing outcomes than needed for the unadjusted estimator to be consistent. The nonparametric bootstrap (bias-corrected and accelerated method) will be used to construct 95% confidence intervals for the average treatment effect. Similar analyses will be conducted for each of the secondary endpoints, along with a gate-keeping multiple testing procedure for an ordered sequence of null hypotheses. ApoE genotyping will be used for post hoc subject stratification. There will be a preplanned subgroup analysis in which each efficacy measure will be looked at separately by ApoE genotype with two subgroups, those carrying one or more ApoE4 alleles and those with no ApoE4 alleles.

Confidential Page 11 of 95

TABLE OF CONTENTS

1	П	NTRO	ODUCTION	21
	1.1	Bac	kground	21
	1.2	Stuc	ly Rationale	21
	1.3	Dos	e Rationale	23
	1.4	Stuc	ly Endpoint Rationale	28
	1.5	Risl	ss and Benefits for Subjects	31
2	S	TUD	Y OBJECTIVES	37
	2.1	Prin	nary Objective	37
	2.2	Sec	ondary Objectives	37
	2.3	Add	litional Secondary Objectives	37
	2.4	Exp	loratory Objectives	37
	2.5	Safe	ety Objective	37
	2.6	Stuc	ly Hypothesis	37
3	Π	NVE	STIGATIONAL PLAN	39
	3.1	Ove	rall Study Design and Plan	39
	3.2	Stuc	ly Duration	40
	3.3	Sele	ection of Study Population	40
	3	.3.1	Inclusion Criteria	40
	3	.3.2	Exclusion Criteria	41
	3	.3.3	Early Termination From Treatment	43
	3.4	Trea	atments	44
	3	.4.1	Details of Study Treatments	44
	3	.4.2	Dosage Schedule	45
	3	.4.3	Treatment Assignment (1:1 Randomization Placebo:AGB101)	45
	3	.4.4	Drug Packaging and Blinding	45
	3	.4.5	Drug Inventory and Accountability	46
	3	.4.6	Treatment Compliance	47
	3	.4.7	Prior and Ongoing Medical History and Treatments	47
	3.5	Ass	essments	47

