3 INVESTIGATIONAL PLAN

3.1 Overall Study Design and Plan

[figure not shown]
This is a multicenter, randomized, double-blind, placebo-controlled, 78-week, fixed-dose study evaluating AGB101 versus placebo as a treatment for slowing the progression of MCI due to AD.

The screening phase will occur 7 days to 42 days before the baseline visit (see Figure 4). After providing informed consent, subjects who meet entry criteria will be randomized 1:1 during the final baseline visit to receive either placebo or AGB101. A total of 160 subjects will be randomized (80/treatment group). Because of the PK and safety profile of AGB101, dosing will be initiated without titration and will be discontinued without tapering.

The baseline visit will occur 1 day before the study start. Subjects will be given their assigned study drug and instructed to take their 1st dose the next morning. A telephone contact will be made 1 week after the baseline visit to assess the subjects' medical status and inquire about any AEs/SAEs; similar telephone contacts will be made at weeks 17 and 56 with the same purpose. Study clinic visits are divided into minor visits ("clinic minor") at weeks 13, 39, and 65 and major visits ("clinic major") at weeks 26, 52, and 78. The difference between these two types of visits is the number and kinds of assessments performed. The "clinic minor" visits consist of a few basic assessments, while the "clinic major" visits consist of more in-depth testing, neuropsychological testing, and blood draws.

Subjects who enroll and subsequently discontinue the treatment before the 78-week visit will be followed up with a phone call at week 78 to assess their medical status and encourage them to come in to complete the early treatment termination/follow-up visit assessments.

Figure 4: Study Schema

Confidential Page 39 of 95

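### Do blocks of 4 or 6 within about 98 sites leave this 160-subject trial no better balanced than coin-flipping?

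*Combined protocol and SAP*

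**What the plan says.** Section 3.4.3 (Treatment Assignment) sets out the scheme: "A central randomization list will be used for the treatment assignment"; the web response system is to "assign the next sequential randomization number within the relevant stratum to the eligible subject"; and "Block randomization will be used at each site, with each block having a randomly chosen length of 4 or 6", the two lengths being equally likely. No stratification factor other than site is named.

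The Synopsis gives the scale: "This study will be conducted at approximately 98 study sites in the Americas and Europe". On sample size, the Synopsis and Section 3.1 both say "A total of 160 subjects will be randomized (80/treatment group"), and Section 3.1 adds that "subjects who meet entry criteria will be randomized 1:1 during the final baseline visit to receive either placebo or AGB101".

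On baseline balance, the Synopsis (Statistical Analyses) prespecifies an intention-to-treat primary estimator that "adjusts for chance imbalances in key baseline variables between the study arms". On genotype it says: "ApoE genotyping will be used for post hoc subject stratification". Nowhere do the documents claim that the blocks are there to balance prognostic factors.

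**The concern.** A permuted block forces equality only at its end. If the average site enrols fewer than two subjects and the shortest block has four places, few blocks will end. The scheme would then look stratified but behave almost like independent coin tosses.

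Two things would be at stake in a trial of this size. The arms could drift well away from 80 each, costing power. And the arms could differ by chance on baseline severity, which no stratum controls, so that the primary comparison would rest on model adjustment alone.

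**Working it through.** **Inputs.** About 98 sites (Synopsis); 160 subjects, 80 per group, 1:1 (Synopsis, Section 3.1); blocks of 4 or 6 with probability 1/2 each, within site (Section 3.4.3). Enrolment per site is not given, so a range is assumed. The documents give no power, effect size or SD, so 160 cannot be re-derived; 80 is 160/2.

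**Step 1: subjects per site.** 160/98 = 1.63. The premise that most blocks stay open is right.

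**Step 2: do open blocks act like a coin?** Let D be the difference in arm sizes. For t subjects in an open block of length b, Var(D) = t(b − t)/(b − 1); for a coin it is t. For two subjects at a site:
- block of 4: 2 × 2/3 = 1.33
- block of 6: 2 × 4/5 = 1.60
- coin: 2

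Equivalently, the chance that both get the same arm is 1/3 or 2/5, on average 0.37, against 0.50 for a coin. So even two subjects in an open block are partly balanced.

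**Step 3: whole trial.** With the most even spread, 62 sites enrol 2 and 36 enrol 1 (62 × 2 + 36 = 160). Then Var(D) = 36 × 1 + 62 × (1.333 + 1.600)/2 = 126.9, so SD = 11.3. For a coin, Var(D) = 160 and SD = 12.65. The uneven patterns were simulated, 4,000 trials each.

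| Accrual over 98 sites (assumed) | Subjects in full blocks | SD of D | Variance relative to coin | Exact 80/80 | 95% range per arm |
|---|---|---|---|---|---|
| Simple randomisation | – | 12.65 | 1.00 | 6.2% | 80 ± 12 |
| Even | 0% | 11.3 | 0.79 | about 7% | 80 ± 11 |
| Random, equal rates | 11% | 9.7 | 0.59 | 8.5% | 80 ± 9 |
| Skewed (Dirichlet shape 1.0) | 32% | 8.2 | 0.42 | 10% | 80 ± 8 |
| Skewed (Dirichlet shape 0.5) | 43% | 7.5 | 0.35 | 11% | 80 ± 7 |

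The site count is approximate. With 60 or 40 sites at equal random rates the variance ratio falls to 0.40 or 0.27.

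**Step 4: cost of unequal arms.** Relative efficiency is 4·n1·n2/N².
- 72/88: 4 × 72 × 88/25,600 = 0.990
- 70/90: 0.984, a variance inflation of 1.6%
- 68/92: 0.978

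If power were 80% at 80/80 (an assumption; two-sided 5%, normal approximation), it would be 79.6% at 72/88 and 79.1% at 68/92.

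**Step 5: is prognostic imbalance caused by open blocks?** Take a factor of 50% prevalence unrelated to site. With an exact 80/80 split and every block full, the SD of the between-arm difference is √(0.25 × (1/80 + 1/80)) = 0.079, or 7.9 points. Simulation of the planned site blocks also gives 7.9 points, and a gap of 10 points or more in about 20% of trials. Completing the blocks changes nothing. The imbalance arises because the factor is not a stratifier, as with any factor left out of a randomisation scheme.

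**Step 6: what does that imbalance cost after adjustment?** With equal arms and a 50% factor, the correlation r between arm and factor equals the gap. In a linear model, adjustment inflates the variance of the treatment effect by 1/(1 − r²).
- 10-point gap: 1/(1 − 0.01) = 1.01, or 1%
- on average: r² is about 0.079² = 0.006, or 0.6%

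That 0.6%, about one subject in 160, is the most that perfect balance on one adjusted factor could save on average. Type I error is not at issue, because chance imbalance is part of the randomisation distribution.

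**The case for a change.** The strongest opposing case is that central blocks within four strata (region by a screening severity factor) would be cheap and visibly tighter. In simulation the SD of the arm-size difference falls to about 2 and the SD of the factor difference from 7.9 to 1.3 points. MMSE and CDR are already measured at screening. Neither the Synopsis nor Section 5.2.6.1 lists the baseline variables to be adjusted for, so the protection relied on in Step 6 is not spelled out. The safety summaries, the ApoE subgroups and the tau PET substudy of about 56 are smaller or described without adjustment.

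Part of this stands. The relevant stratum in Section 3.4.3 is undefined and the adjustment variables are unnamed. That is missing detail, and Section 5.2 defers the detailed analysis to a SAP to be signed before database lock. It does not show that the allocation scheme fails. A central list held in a web system can also contain site blocks, so those two statements do not conflict.

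The rest is a trade. The drop to 1.3 points applies only to the chosen stratifier; unrelated factors stay near 7.9. Giving up site blocks also gives up the partial within-site balance of Step 2. That has some value here: the primary endpoint is an interview-based rating (Section 1.4) and MRI runs on several vendors' scanners (Section 8.3.2), so variation between sites is plausible. Finally, this is version 6.1 of December 2020, with COVID-19 provisions in Section 5.2.1. If many subjects are already randomised, a new list would reach only the remainder.

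**Conclusion.** The concern does not hold. Its factual base is correct: 1.6 subjects per site, mostly open blocks, and no named stratifier beyond site. The two conclusions drawn from it are not. Site blocking does better than a coin on arm size under every accrual pattern examined. Equal group sizes are a plan under 1:1 allocation, with no promise of an exact split, and the likely departures cost less than one point of power. Prognostic balance at the level of chance is the normal result of not stratifying on a factor and has nothing to do with whether blocks fill; for adjusted factors the primary analysis absorbs it at a cost of about 0.6% of variance.

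This rests on assumed accrual patterns, since enrolment per site is not given; on an assumed 80% power for the efficiency figures; on a linear-model approximation to the planned estimator; and on the important prognostic variables being among those adjusted for. Central stratification would be a defensible alternative, but its absence does not weaken the primary result.

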3.4.4 Drug Packaging and Blinding

The double-blind study drug will be packaged, labeled, and distributed to study sites by a designated vendor.

The study drug supplied to subjects will be packaged in 3 bottles containing 34 tablets each. The study drug package labels will be in compliance with applicable regulatory requirements and will include the statements "Keep out of reach of children", "Caution: New Drug – Limited by Federal (United States) law to investigational use", and/or "For clinical trial use only" as appropriate, as well as any other locally mandated statements. Labels will be translated into the local language.

At a minimum, labels will also include the following information: the name of the sponsor, study code, a unique identifier number, and appropriate contact information. A re-test or expiry date will be included in jurisdictions that require this information.

The investigator may unblind a subject's treatment assignment. If that happens, the following will apply:

Such a measure should be taken **only in the case of an emergency** OR in the event of a serious medical condition when knowledge of the study drug is essential for the appropriate clinical management or welfare of the subject, as judged by the investigator.

Confidential Page 45 of 95

In the event that a medical emergency or condition requires knowledge of the subject's treatment assignment, the investigator will contact the medical monitor to discuss the potential need for unblinding. Unblinding will be done through the interactive voice response system/IWRS. The procedure for subject unblinding is provided in the study reference manual.

If, for safety reasons, the investigator determines that the subject's treatment must be immediately unblinded to provide adequate medical treatment, the investigator must inform the medical monitor about the unblinding as soon as possible, but without revealing the treatment assignment of the unblinded subject.

The sponsor will be informed immediately of the decision to unblind any subject and will determine whether any additional measures need to be taken for the safety of subjects currently in the study.

Any other requests to reveal a subject's treatment identity must be requested from and approved by the sponsor.

A subject will be withdrawn from the study if his or her treatment code is unblinded by the investigator. The date, time, and reason for the unblinding must be fully documented in the source documents and the eCRF.

The sponsor, or designee, may unblind the treatment assignment for any subject if this is required to fulfill regulatory reporting obligations, such as expedited SAE reporting.

Information about any subject for whom a code break or unblinding occurs will be provided to the Data Safety and Monitoring Board (DSMB) by the sponsor, or designee, within 15 days (within 7 days in the event of a fatal event).

Information regarding unblinding treatment allocation in relation to reporting Suspected Unexpected Adverse Reactions (SUSARs) is provided in Section 4.4.1.

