3.3.3 Early Termination From Treatment

A subject who discontinues from treatment will complete the early termination visit assessments as shown in Table 7. The investigator will make every attempt to follow the subject to week 78 and complete the early termination/follow-up visit.

A termination electronic case report form (eCRF) page should be completed for every subject who receives the study drug, whether or not the subject completes the study. The reason for early termination should be indicated on this form. The primary reason for early termination should be selected from the following standard categories:

Adverse event (adverse reaction): Clinical or laboratory events occurred that, in the medical judgment of the investigator for the best interest of the subject, were grounds for discontinuation. This includes serious and non-serious AEs regardless of relation to the study drug.

Death: The subject died.

Withdrawal by subject: The subject or legal representative desired to withdraw from further participation in the study in the absence of an investigator-determined medical need to withdraw. If the subject gave a reason for withdrawing, it should be recorded in the eCRF.

Withdrawal by study partner: The study partner desired to withdraw from further participation in the study in the absence of an investigator-determined medical need to withdraw. If the study partner gave a reason for withdrawing, it should be recorded in the eCRF.

Lack of Efficacy: The subject or legal representative (or study partner) indicated a lack of efficacy as the primary reason warranting discontinuation from the study.

Noncompliance with study drug: The subject was noncompliant in taking the prescribed study drug. Efforts to ensure compliance with the protocol including reminders, phone calls, and counseling should be recorded. Subjects who discontinue treatment will not be automatically discontinued from the study. Every effort should be made to bring subjects back for study visits unless the subject withdraws consent.

Confidential Page 43 of 95

Physician decision: The study physician may determine that the subject should no longer continue in the study if continuation would pose a safety risk for either the subject, study partner, or another person. In this case, the reason for the concern should be recorded.

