Visit type	С	I	I	C major	T ⁶	C minor	T ⁶	C major	C minor	C major	T ⁶	C minor	C major	C major	T/C
[¹⁸ F]MK-6240 (Tau protein marker, optional)				X ¹⁰									X^{10}		
fMRI (JHU only) ¹²			X					X							
Study drug dispensing				X ¹³		X		X	X	X		X			
PK sampling								X		X			X	X	
Biomarker Blood Draw													X	X	
Prior/Concomitant medications ¹⁴	X														
AE/SAE reporting		X													

Abbreviations: AE=adverse event; ApoE=apolipoprotein E; B=baseline; B MRI=baseline magnetic resonance imaging; BPS-O=Behavioral Pattern Separation-Object; C=clinic visit; CBC=complete blood count; CDR=Clinical Dementia Rating; C major=major clinic visit; C minor=minor clinic visit; C-SSRS=Columbia Suicide Severity Rating Scale; D=day; DNA = deoxyribonucleic acid; ECG=electrocardiogram; ET=early termination; FAQ=Functional Activities Questionnaire; FLAIR=fluid attenuation inversion recovery; fMRI = functional magnetic resonance imaging; GDS=Geriatric Depression Scale; HIS=Hachinski Ischemic Scale; I=imaging visit; IR-SPGR=radiofrequency-spoiled gradient echo; ISLT=International Shopping List Test; JHU = Johns Hopkins University; M=month; MMSE=Mini Mental State Examination; MP-RAGE=magnetization-prepared gradient echo; MRI=magnetic resonance imaging; N/A=not applicable; PET=positron emission tomography; PK=pharmacokinetic; S=screening; SAE=serious adverse event; T=telephone contact; T/C=telephone contact/clinic visit; W=week.

The screening phase (S1, S2, S3/B MRI) will occur 7 days to 42 days prior to baseline. Subjects must meet all the criteria during all the screening visits in order to be enrolled in the study. Height without shoes will be recorded in inches or meters.

Baseline visit will occur on day -1 within 12 days ± 2 days of the S3/B MRI visit. S3/B MRI will occur up to 2 weeks prior to Baseline; the Tau scan needs to occur 1 or more days before the cognitive visit.

Week 1 visit will occur 7 days after the baseline visit.

- ⁴ Subjects who discontinue treatment early (ie, at any time after randomization) will have the early termination visit assessments performed as soon as possible after treatment termination.
- All subjects who enroll and subsequently discontinue treatment will be followed up with a phone call during week 78 to assess their medical status and encourage them to come in for a final CDR and neuropsychological assessments and AE reporting.

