3.5.3 Early Termination Visit and Early Termination/Follow-up Visit

Subjects who discontinue treatment (ie, at any time after randomization and before the week 78 visit) will have the early termination visit assessments performed as soon as possible after treatment termination. In addition, all subjects who enroll and subsequently discontinue will be followed up with a phone call during week 78 to assess medical status and encourage them to come in to complete the early termination/follow-up visit assessments.

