3.5.3.2 Early Termination Follow-up Visit (Week 78)

- Vital signs and body weight
- ISLT, MMSE, GDS, BPS-O task, FAQ, CDR (participant and study partner), and C-SSRS
- AEs/SAEs and concomitant medication reporting

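### After an investigator code break, section 3.4.4 withdraws the subject from the study while other sections seek a week-78 CDR after discontinuation; the plan does not say which applies (small effect, cheap to settle)

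*Combined protocol and SAP*

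**What the plan says.** Section 3.4.4 allows the investigator to break the code only in an emergency or a serious medical condition where knowing the assignment is essential. The consequence is: "A subject will be withdrawn from the study if his or her treatment code is unblinded by the investigator". The same section adds: "The date, time, and reason for the unblinding must be fully documented in the source documents and the eCRF". It mentions no early termination visit, week-78 call or CDR. For the unblinding procedure it refers to the study reference manual, which is not among the documents.

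For subjects who stop treatment, four places seek follow-up to week 78:

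- Section 3.1: "Subjects who enroll and subsequently discontinue the treatment before the 78-week visit will be followed up with a phone call at week 78", with encouragement to attend the follow-up assessments.
- Section 3.3.3: "The investigator will make every attempt to follow the subject to week 78 and complete the early termination/follow-up visit".
- Table 7, footnote to the early termination/week-78 column: subjects are called in week 78 to "encourage them to come in for a final CDR and neuropsychological assessments and AE reporting".
- Section 3.5.3: "all subjects who enroll and subsequently discontinue will be followed up with a phone call during week 78". This sentence speaks of discontinuing without the word treatment. Section 3.5.3.2 lists the content of the visit: "ISLT, MMSE, GDS, BPS-O task, FAQ, CDR (participant and study partner), and C-SSRS", plus adverse event reporting.

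Table 7 also marks the CDR at the early termination visit, and section 3.5.3 places that visit as soon as possible after treatment ends.

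On analysis, section 5.2.1 defines the full analysis set as all randomized subjects, analysed as randomized. The Synopsis says the primary estimator adjusts for week-78 outcomes missing at random.

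**The concern.** Sections 3.4.6 and 5.2.2 keep leaving treatment and leaving the study apart: stopping treatment does not automatically end participation. Section 3.4.4 uses the stronger term, study withdrawal. A site that takes it at its word would have no reason to seek the week-78 CDR.

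The primary outcome would then go unsought because of a protocol rule, after a health event that followed randomization. That differs from the loss to follow-up that the Synopsis gives as the source of missing data, and it makes missing at random harder to defend for these subjects. The pattern-mixture analysis in 5.2.6.3 can show how large a departure would change the conclusion. It cannot recover a value that nobody tried to collect. The scheduled adverse event review at the follow-up visit would be lost as well.

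**Working it through.** **Text comparison.**

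1. *Does any follow-up text exempt code-break subjects?* No. Sections 3.1, 3.3.3 and 3.5.3 and the Table 7 footnote contain no such exemption.
2. *Does 3.4.4 refer to the follow-up text?* No. It requires documentation of the code break and stops there.
3. *Does any text set precedence?* No. The rest of the unblinding text (end of 3.4.4, and 4.4.1) and the analysis text (5.2.1, 5.2.2, 5.2.6.3) do not say how such a subject is followed. In 3.4.6 and 5.2.2 the only stated exception to bringing subjects back is withdrawn consent, but that wording sits in text on noncompliance.
4. *Result.* Two readings remain open. Either 3.4.4 is a specific rule on leaving the study and overrides the rest, or the subject also counts as having discontinued and the week-78 visit is still sought.

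**Size.** The plan has no figure to reproduce: it gives no code-break rate, SD, effect size or dropout rate. From the documents: 80 per arm (3.1), a 5% significance level (5.2.6.2) and a two-sided alternative (Synopsis). Assumed: SD of the CDR-SB change 1.5 to 2.5 points; 20% loss, so 64 completers per arm; k subjects lost to the rule in an arm; and d, the distance in points of their true change from the missing-at-random prediction.

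Standard error = SD × √(2/64):

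| SD | 1.5 | 2.0 | 2.5 |
|---|---|---|---|
| SE | 0.265 | 0.354 | 0.442 |

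Net bias = (k_A·d_A − k_P·d_P)/80, with A for AGB101 and P for placebo. Type I error at bias/SE = δ is P(|Z + δ| > 1.96).

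| Case | Bias (points) | Bias/SE, SD 1.5 to 2.5 | Type I error |
|---|---|---|---|
| No code breaks, or 2 v 2 losses at d = 2 | 0 | 0 | 5.0% |
| One excess loss, d = 1 | 1/80 = 0.0125 | 0.047 to 0.028 | 5.0% |
| 3 v 1 losses, d = 2 | (6 − 2)/80 = 0.05 | 0.189 to 0.113 | 5.4% to 5.2% |

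A bias of 0.25 SE (type I error 5.7%) needs 0.25 × SE × 80/d excess losses. At d = 1 this is 5.3, 7.1 and 8.8, so 6 to 9 subjects. At d = 2 it is 2.7, 3.5 and 4.4, so 3 to 5 subjects.

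Power: at the difference that gives 80% with 64 completers per arm, 63 per arm gives 79.4%.

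**The opposite error.** If values obtained after a code break are used, they may be informed. With one subject per arm, shifted by an assumed 0.5 points in opposite directions, the bias is (0.5 + 0.5)/80 = 0.0125, or (0.5 + 0.5)/64 = 0.0156 if completers are weighted up. The larger value is 0.059 to 0.035 SE. It does not cancel when code breaks are balanced between arms.

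**The case against.** The strongest reply is that the protocol already covers these subjects. Section 3.5.3 speaks of all who discontinue, and a subject withdrawn from the study would ordinarily also stop study drug and so fall under the Table 7 footnote. An early termination CDR would then be obtained close to the code break, in addition to any from weeks 26 and 52. This is a fair reading, and it stands as a reason to expect a small effect. It does not settle the matter, because the sentence in 3.5.3 follows one on treatment discontinuation and neither text mentions code breaks. The documents also do not list the estimator's post-baseline inputs, so how far an early CDR would help is unknown.

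A second reply is that a CDR after a code break may be biased, since it rests on interviews with the subject and study partner (1.4, 3.5.4.1). That is true, and the error is of the same order as the one from missingness. It bears on how the value is analysed rather than on whether to collect it: a collected value can be set aside later.

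A third is that code breaks reach the medical monitor and the sponsor promptly under 3.4.4, so divergent site practice can be corrected. This also stands. That sites would in fact diverge is a possibility the documents do not establish.

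A reader might also infer from 3.3.3 that code-break subjects have no place in the termination form. That section says "The primary reason for early termination should be selected from the following standard categories", and none of the 11 names a code break. But the adverse event category would often fit and there is a category for other reasons, so the list does not show that these subjects are left out.

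**Conclusion.** The ambiguity is real and concerns collection of the primary outcome in an intention-to-treat analysis, so it is worth settling. The severity is low. Under the assumptions above, one excess loss moves the estimate by about 0.01 points with type I error still about 5.0%, and several excess losses in one arm are needed to reach even 5.7%. The SD, the 20% loss, k, d and the 0.5-point rating shift are all assumed.

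Three stronger conclusions that a reader might draw are not supported:

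- *That the week-78 CDR is definitely forgone, or that the sections flatly contradict each other.* The follow-up texts can be read to include these subjects, and the study reference manual may address the point.
- *That code-break subjects leave the analysis.* They remain in the full analysis set under 5.2.1, and no text removes data already collected. Unblinding by the sponsor for regulatory reporting carries no withdrawal rule.
- *That safety follow-up ends.* Known adverse events are followed until resolved or stable (sections 4 and 4.2.2), and some later related events remain reportable (4.2.1, 4.2.2). Only the scheduled ascertainment is in doubt.

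**What to change.** Reconcile 3.4.4 with 3.1, 3.3.3, Table 7 and 3.5.3. State that an investigator code break does not by itself end outcome and adverse event collection, and that the early termination and week-78 follow-up assessments are still sought unless consent is withdrawn.

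Flag CDR values obtained after the recorded code-break date. In the SAP, which section 5.2 requires to be signed before the code is broken for all subjects, keep these values in the primary full-analysis-set analysis, in line with the intention-to-treat principle in 5.2.1. Add a sensitivity analysis that sets them to missing.

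No rule on study drug after unblinding is proposed; the sponsor must reconcile the passages on that point.

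The cost is about one sentence in 3.4.4 and one in the SAP, for probably very few subjects. Both visits already exist. The code-break date and time are already recorded, so the flag follows from comparing them with visit dates. The downside is that a few CDR ratings may be informed by knowledge of the assignment; the sensitivity analysis addresses that. A separate unaware rater is not requested: about 98 sites for 160 subjects is 160/98 ≈ 1.6 subjects per site, so one may often be unavailable, and it would not blind an informed study partner.
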